30 freshly extracted permanent teeth with MIH will be collected from the pediatric clinics of the University of Texas Health San Antonio (UTHSA). These teeth were extracted as part of the patient's standard of care and

donation will be done based on the patients willingness. If the patient wishes to donate the teeth, they will be placed in a container within the pediatric dental clinics and will be donated without identifiable information attached to them. The teeth will be cleaned of debris/stains and examined with a transilluminator. Teeth with MIH but free of caries or other malformations will be selected and cleaned with pumice to remove the pellicle. Using a water-cooled diamond wire saw, 3 blocks, two from MIH affected area and one from a healthy area will be produced from each tooth, with each block measuring approximately 2 mm length x 2 mm width x 1 mm thickness. The cut will take place so that the different layers from the outer surface to the inner surface present in each block are: outer enamel surface, enamel, dentino-enamel junction (DEJ) and dentin.

Measurement of baseline mineral density of the tooth blocks

Micro computed X-ray tomography (μ -CT) is a high resolution, non-destructive radiographic method of analysis that generates qualitative images and quantitative analysis of the mineral density (MD) in tooth samples. For this reason, images will be collected from the samples to measure the mineral density of the MIH enamel lesions before (MD_b) and after (MD_t) remineralization treatment as well as the mineral density (MDs) of healthy enamel samples. The μ -CT scanning and analysis procedure will be performed as described in our previous publications.¹⁷

Study Population/Participants

Fifteen subjects (8 females, 7 males) will be recruited into the study. The subjects to be included should be 18 to 60 years old in good general health with no known history of allergy to personal care/consumer products. They must have a minimum of 20 natural uncrowned teeth (excluding third molars), no active unrestored cavities and a normal salivary flow rate (stimulated and unstimulated flow of ≥ 0.7 ml/min and ≥ 0.2 ml/min respectively) ascertained from a preliminary sialometry test. They also should give written informed consent, be available throughout entire study, and be willing to wear intra-oral appliance 24 hours per day and use only assigned products for oral hygiene throughout the duration of the study.

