At every visit, the dental examiner will visually examine the soft and hard tissues of the oral cavity and peri-oral area using a dental light and dental mirror. Additionally, subjects will be asked about and examined for any adverse events. Subjects may call and request a visit for any concern of potential adverse event.

Data Handling

Using the μ CT images, the pattern and the extent of remineralization produced within each lesion by each treatment product will be examined and described. This will be clearly shown by comparing the pre- and post-test images side-by-side. For all calculations, the absolute MD will be measured and used. For the remineralization blocks, the values of the MD_b and MD_t for each test product will be compared using paired t-test to determine any significant change (remineralization) made by the test product (intra-group comparison). However, to make comparisons between the two products (intergroup comparison), percentage change in MD calculated relative to the control will be determined for each test product as such: % Change in MD (% Δ MD) = [(MD_b – MD_t)/MD_b] x 100

The percentage MD recovery following remineralization will be calculated as follows:

% MD recovery (%MDR) = [(B-T)/(B-S)] x 100, with S = mean MDs of healthy enamel blocks, B = mean MD_b of MIH enamel blocks before remineralization, and T = mean MD_t of MIH enamel blocks after intra-oral exposure.

Sample Size Calculation

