The power analysis and sample size calculation were performed using nQuery Advisor software (Statistical Solutions, Cork, Ireland). The sample size for this study is based on the primary efficacy parameter, % MDR following 2 weeks of treatment. A sufficient number of subjects will be screened to randomize approximately 15 subjects with the intention that approximately 15 subjects complete all study treatments and be evaluable for the efficacy analysis. With these conditions met, the study will have 80% power at the 5% significance level, using two-sided testing, to detect a mean treatment difference in %MDR of approximately 8.1% assuming a within subject standard deviation of approximately 12.6%. In the absence of available 2 week data from previous mineral density studies, the within subject standard deviation has been estimated using 14-day post-treatment data from a previous results obtained by this group in a demineralization and remineralization study using HAP toothpaste¹⁵. In that study the mean % change in mineral loss was equal to 30.3 with a standard deviation equal to 16.3.

Statistical Analysis

After assumptions of normality and homogeneity of variances have been verified by normal probability plots, comparisons of the mean values of MD, %ΔMD and %MDR between the two treatment groups as well as the intra-group comparisons will be performed using the paired Student's t-test (STATA version 10.0, StataCorp LP, USA) at a significance level of 5%. The primary endpoints of the present study are expected to be enhanced remineralization of MIH lesion.

E. References

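### Raw mineral density is listed, unranked and unadjusted for baseline, as one of three HAP-versus-fluoride tests; a baseline-adjusted comparison should replace it

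*Combined protocol and SAP*

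**What the plan says.** Statistical Analysis states that "comparisons of the mean values of MD", along with those of %ΔMD and %MDR, "between the two treatment groups as well as the intra-group comparisons will be performed using the paired" Student's t-test, at a 5% level. The three measures carry no order of importance in that sentence, and no covariate is mentioned.

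The baseline is available for every block: the micro-CT scans are there to "measure the mineral density of the MIH enamel lesions before (MD_b) and after (MD_t) remineralization treatment" (Measurement of baseline mineral density of the tooth blocks).

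Two other sections bear on how the product comparison is meant to work:

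- Data Handling assigns the comparison of MD_b with MD_t to the within-product test. For the product comparison it says that "to make comparisons between the two products (intergroup comparison), percentage change in MD calculated relative to the control will be determined for each test product", with the formula "MD_b – MD_t)/MD_b] x 100".
- Sample Size Calculation states: "The sample size for this study is based on the primary efficacy parameter, % MDR following 2 weeks of treatment". The %MDR formula in Data Handling also subtracts baseline: (B−T)/(B−S) × 100.

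**The concern.** Post-treatment MD of a block is its starting MD plus whatever it gained. The paired t-test removes differences between subjects, but the blocks come from donated teeth, not from the subject wearing the appliance. If the two phases use different teeth, the within-subject difference in MD_t also contains the difference in starting density between two unrelated teeth. By the background section's own means, mild and moderate/severe lesions differ by 0.31, and the plan neither restricts nor balances severity.

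At stake is one of the three tests that could be cited on null hypothesis 2. A non-significant raw-MD result would say little, yet nothing in the plan ranks it below the other two.

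**Working it through.** **The plan's own figure.** The stated power is 80% for 8.1 points of %MDR, with n = 15, two-sided 5% and within-subject SD 12.6. The paired t-test (noncentral t, 14 df) gives 63.9% if 12.6 is the SD of the paired differences. It gives 37.5% if 12.6 is the within-subject SD, so that the SD of differences is 12.6 × √2 = 17.8. Neither reproduces 80%. That is a separate matter, but it sets the ceiling here: on the plan's wording (within-subject SD), a baseline-using test can be expected to reach about 37%.

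**Inputs from the documents.** Mean MD is 2.51 healthy, 2.24 mild and 1.93 moderate/severe (background). The effect is 8.1 points, with SD 12.6 within subject and 16.3 in the earlier study (Sample Size Calculation). The between-subject SD is then √(16.3² − 12.6²) = 10.3.

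**Assumed.** The SD of MD_b within a severity class is 0.05–0.15, and different teeth serve the two phases. The documents give neither.

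**Effect in density units.** Deficits are 2.51 − 2.24 = 0.27 and 2.51 − 1.93 = 0.58. The effect is 0.081 × 0.27 = 0.022 (mild) to 0.081 × 0.58 = 0.047 (severe).

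**Hand check (constant gain).** The SD of the raw-MD difference is √[2·SD_B² + 2·(0.126 × deficit)²]. For mild teeth with SD_B = 0.10, this is √(0.0200 + 0.0023) = 0.149. The SE is 0.149/√15 = 0.039, against an effect of 0.022, and power is 8.3%. The baseline term is 0.0200/0.0223 = 90% of the variance. For severe teeth with SD_B = 0.05 it is only 0.0050/(0.0050 + 0.0107) = 32%, and power is 27%.

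**Simulation.** 20,000 trials per setting, n = 15, recovery 20.3% versus 28.4%, one value per subject and phase, baselines capped just below healthy density. The adjusted analysis regresses the within-subject difference in MD_t on that in MD_b and tests the intercept. In each cell, the first figure has gain proportional to the deficit and the second has constant gain.

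| Teeth | SD of MD_b | Raw MD % | Adjusted % | %MDR per block % | %ΔMD % |
|---|---|---|---|---|---|
| Mild | 0.05 | 19.0 / 15.1 | 33.0 / 34.8 | 36.5 / 31.2 | 31.3 / 37.2 |
| Mild | 0.10 | 10.4 / 8.3 | 30.0 / 35.5 | 37.4 / 15.5 | 22.2 / 37.5 |
| Mild | 0.15 | 7.9 / 6.5 | 26.4 / 34.1 | 37.5 / 5.6 | 16.3 / 36.0 |
| Half/half | 0.05 | 9.8 / 8.1 | 29.7 / 35.4 | 37.4 / 21.7 | 20.7 / 36.6 |
| Half/half | 0.10 | 9.1 / 7.6 | 28.1 / 34.6 | 37.6 / 13.6 | 18.4 / 35.8 |
| Half/half | 0.15 | 7.8 / 6.8 | 26.6 / 35.2 | 37.1 / 6.3 | 16.0 / 35.9 |
| Severe | 0.05 | 30.3 / 27.6 | 34.2 / 35.2 | 36.9 / 36.2 | 35.0 / 37.5 |
| Severe | 0.10 | 20.7 / 16.0 | 34.0 / 35.4 | 37.6 / 32.4 | 30.9 / 37.3 |
| Severe | 0.15 | 14.4 / 11.0 | 32.2 / 35.0 | 37.6 / 26.4 | 25.6 / 35.9 |

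With no product effect, the raw and adjusted tests both reject in 4–5% of trials. Figures move by a point or two with simulation details. The lowest %MDR values depend on how blocks with almost no deficit are handled.

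**Sensitivity.** If 12.6 is instead the SD of paired differences, raw-MD power is 43–58% at a baseline SD of 0.02, 17–39% at 0.05 and 8–19% at 0.10, while a change score or %ΔMD has 62–64%. If the starting densities in the two phases have correlation ρ, as with sister blocks of one tooth, the baseline term shrinks to 2·SD_B²·(1 − ρ), and the loss shrinks with it.

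**The case against.** The strongest reply is that the plan already uses baseline where it counts. Data Handling names %ΔMD for the product comparison, %MDR is the primary efficacy parameter, and both have the change in the numerator. The 8.1-point effect is defined on %MDR. A reader might infer from the first words of the analysis sentence that the HAP-versus-fluoride test as a whole ignores baseline, or that tooth-to-tooth variation swamps the planned effect. The documents do not support either reading, and this part of the reply stands in full.

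A reader might also infer that chance imbalance in baselines would generate false product differences. It does not do so beyond the nominal rate: type I error is about 5% with or without adjustment. The cost is power.

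It is also fair that one of the planned ratios does as well as or better than the covariate model in every setting of the table. But which one depends on how gain relates to baseline. %MDR does best when gain is proportional to the deficit; %ΔMD does best when gain is constant. Each can lose much of its power under the other form. The background section says the use of HAP for this purpose has not been studied, so the form is not known in advance. The covariate model is the steadier choice, not always the best one.

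Finally, the size depends on a baseline SD and a tooth allocation that the plan omits. Thirty teeth with two lesion blocks each would fit 15 subjects × 2 phases × 2 sides = 60 blocks, but no text says which tooth goes to which phase.

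**Conclusion.** The point holds for the raw-MD comparison only. As written, that test is unranked and unadjusted although MD_b is scanned for every block. Under different teeth per phase and an assumed baseline SD of 0.05–0.15, it has roughly a quarter to a half of the adjusted analysis's power for mild or mixed teeth. For all-severe teeth the loss runs from slight to about two thirds. It is smaller still if baselines are uniform or sister blocks serve both phases.

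The primary comparison is not shown to ignore baseline. One wording leaves a loose end: "B = mean MD_b of MIH enamel blocks before remineralization" does not say whether %MDR is formed per block or from pooled means. If a pooled B were combined with individual T, %MDR too would become a raw comparison. The text does not state that, so it is a matter to clarify and not part of this conclusion.

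**What to change.** In Statistical Analysis, remove MD from the list of between-product tests and keep raw MD as a descriptive summary by product. In its place, compare MD_t between products with product as fixed effect, subject as random effect and the block's own MD_b as covariate. Alternatively, regress the within-subject difference in MD_t on the within-subject difference in MD_b and read the product effect at zero baseline difference. Report the adjusted difference with its 95% CI beside %MDR, which stays the primary efficacy parameter.

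The cost is a sentence or two of analysis text and one degree of freedom (critical t 2.160 on 13 df instead of 2.145 on 14 df), with no new data. If gain is truly proportional to the deficit, the adjusted analysis has lower power than %MDR: about 26–34% against 37–38% in the settings above. The change does not bring the trial to its stated 80% power.

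### The plan names two different measures for the product comparison and tests three at 5% each, with no rule for which one decides null hypothesis 2

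*Combined protocol and SAP*

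**What the plan says.** Null hypothesis 2 (section A) concerns a difference in effectiveness between the two toothpastes and names no measure. Four later statements in section D bear on how it will be tested:

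- **Data Handling:** "to make comparisons between the two products (intergroup comparison), percentage change in MD calculated relative to the control will be determined". This is percentage change in MD (%ΔMD).
- **Sample Size Calculation:** "The sample size for this study is based on the primary efficacy parameter, % MDR following 2 weeks of treatment". For that measure, "the study will have 80% power at the 5% significance level, using two-sided testing".
- **Statistical Analysis, tests:** comparisons of MD, %ΔMD "and %MDR between the two treatment groups as well as the intra-group comparisons will be performed" as paired t-tests at 5%. No testing order, adjustment or decision rule is given.
- **Statistical Analysis, endpoints:** "The primary endpoints of the present study are expected to be enhanced remineralization of MIH lesion". The endpoints are plural, and no measure is named.

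Data Handling also gives the formulas. %ΔMD is computed from MD_b and MD_t. %MDR is computed from B, T and S, which are defined as means over blocks.

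**The concern.** The trial makes one comparative claim from 15 subjects, and that claim should rest on one pre-specified test. As written, the answer to null hypothesis 2 could come from %ΔMD (following Data Handling), from %MDR (following the sample size text), or from any of the three measures listed under Statistical Analysis. These measures can disagree. If the significant one is picked after the results are seen, 5% is no longer the error level of the conclusion.

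**Working it through.** **Inputs from the protocol.** 15 subjects, so 15 pairs; two-sided 5% per test; SD 12.6 and difference 8.1 for %MDR (Sample Size Calculation). Three between-product measures (Statistical Analysis). Mean densities of 2.24 (mild), 1.93 (moderate/severe) and 2.51 (normal) (Significance / Background). The documents give no correlation between the measures.

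**1. The plan's own figures.** In simulated trials with no product difference, each single test rejected in 4.5% to 5.4% of runs, so the 5% level holds for one measure on its own. The stated 80% power for %MDR is not reproduced. A two-sided paired t-test gives 63.9% if 12.6 is the SD of the difference, and 37.5% if it is the within-subject SD (SD of difference 12.6 × √2 = 17.8). That is a separate matter and does not affect the false-positive rate.

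**2. Which measure decides.**

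| Place | Measure for the product comparison |
|---|---|
| Data Handling | %ΔMD |
| Sample Size Calculation | %MDR |
| Statistical Analysis, tests | MD, %ΔMD and %MDR |
| Statistical Analysis, endpoint sentence | none named |

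**3. How closely the two conflicting measures agree.** For a single lesion, %ΔMD = 100(B − T)/B and %MDR = 100(B − T)/(B − S), so %MDR/%ΔMD = B/(B − S).

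- Average mild lesion: 2.24/(2.24 − 2.51) = 2.24/(−0.27) = −8.3.
- Average moderate/severe lesion: 1.93/(1.93 − 2.51) = 1.93/(−0.58) = −3.3.

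The numerator is shared, so the measures are strongly related. The sign is opposite, which does not matter for a two-sided test. They are not interchangeable: the same percentage change is worth about 8.3 points of %MDR in a mild lesion and 3.3 in a severe one.

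**4. Ceilings if any significant result counts.**

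- Three independent tests: 1 − 0.95³ = 14.3% (Bonferroni bound 3 × 5% = 15%).
- Two independent tests: 1 − 0.95² = 9.75%.

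**5. Effect of correlation.** For three equally correlated paired t-tests with 15 pairs (200,000 runs), the any-of-three rates were:

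| Correlation | 0.5 | 0.7 | 0.8 | 0.9 | 0.95 | 0.99 |
|---|---|---|---|---|---|---|
| Rate | 12.8% | 11.2% | 10.1% | 8.5% | 7.5% | 6.2% |

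**6. Simulation from the plan's formulas** (20,000 runs per setting, %MDR taken per subject). Baseline means were 2.24, 1.93 and their midpoint 2.085. Assumed inputs were block SD 0.02, 0.05 or 0.08; mean recovery 10% or 30%; and recovery SD 12.6 or 12.6/√2 = 8.9.

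- Any of three: 6.2% to 12.3%.
- %ΔMD or %MDR only: 5.1% to 8.4%. Their absolute correlation was 0.62 to 1.00.

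Further runs varied the tooth allocation. With different teeth in each phase, tooth SD 0.05-0.08, and mild-only or half-severe lesions, any-of-three was 10.2% to 12.6%. All-severe lesions gave 8-10%. Splitting one tooth's blocks across the phases gave 6-8%. For the two conflicting measures, different teeth gave about 6-9% and same-tooth blocks 5-7%.

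The block count is 30 teeth × 2 = 60 = 15 subjects × 2 phases × 2 sides. That fits one tooth per appliance, but the plan does not state the allocation.

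Across all runs the range is roughly 6-13% for any of three, and 5-9% for the two in conflict.

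**The case against.** The strongest reply is that the plan does name a primary measure: the study is sized on %MDR, and the later endpoint sentence offers no rival. If that is honoured, the primary test stays at 5%. This stands as arithmetic. It does not settle the text, because the label appears only in the sample size paragraph, while the sentence that assigns a measure to the product comparison assigns %ΔMD.

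A second reply is that only %ΔMD and %MDR conflict and that they are strongly correlated. This also stands, and it is why the smaller range applies to that conflict. Raw MD is listed among the between-product tests, but nothing makes it decisive, and Data Handling uses it for the before-after comparison within a product.

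A reader might infer that the trial's false-positive rate is 10-13%. The documents do not support this. It needs an any-of-three rule that the plan does not state, different teeth in each phase, and assumed tooth SDs and correlation. Some runs behind that range also used 16.3 as an SD for %MDR, whereas the plan gives 16.3 as the SD of percentage change in mineral loss in an earlier study.

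Two further limits apply. Read literally, %MDR yields one value per product and cannot enter a paired t-test; two tests then remain, with the 9.75% ceiling. The within-product tests do not add to the rate of false product differences.

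The product code is withheld until the data have been interpreted. This limits choosing a measure to favour a known product, but not choosing the measure that shows a difference.

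**Conclusion.** The inconsistency stands on the text alone and needs no simulation: two sections point to different measures, a third tests three at 5% each, and no rule says which decides null hypothesis 2. The size depends on how the results would be used:

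- %MDR alone honoured as primary: 5%.
- Either of the two conflicting measures accepted: roughly 5-9%, ceiling 9.75%.
- Any of the three accepted: above 5%, at most about 14%, and roughly 6-13% in simulation.

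The two simulated ranges rest on assumed tooth allocation, lesion mix, block SD and recovery, and on a per-subject %MDR that the plan does not yet define. They show what the open choice could cost; they are not the plan's established error rate.

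**What to change.** 1. In Statistical Analysis, name one primary product comparison: the within-subject difference in %MDR between products, two-sided at 5%. This follows the plan's own sample size basis.
2. In Data Handling, redefine %MDR for each subject and phase. This is a real change of definition, since B, T and S are now group means. State how the two blocks on one appliance are combined and which healthy-enamel value serves as S.
3. Change the intergroup sentence in Data Handling so that it refers to %MDR, and replace the plural endpoint sentence with the named measure.
4. Report %ΔMD and raw MD between products as supportive, with estimates and 95% confidence intervals and no separate claim of a product difference.

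This is a wording change to be made before the product code is opened. It adds no subjects, visits or measurements. The cost is that a significant result on %ΔMD or raw MD alone can no longer support a claim of a product difference.

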The exclusion criteria are having advanced periodontal disease, a medical condition that requires premedication prior to dental visits/procedures, an impaired salivary function, wearing an orthodontic retainer(s), not having enough teeth to secure the oral appliance, having diseases of the soft or hard oral tissues, using drugs that can affect salivary flow, using antibiotics one month prior to or during this study, participating in another clinical study one week prior to the start of the washout period or during this study period, using tobacco products, having an allergic

history to common toothpaste ingredients, and having a compromised immune system (HIV, AIDS, immuno-suppressive drug therapy) as determined by review of medical history

Recruitment of Study Subjects

This is a double-blind, randomized, crossover, single center, controlled clinical trial. The study will be blinded to both the study team and the subjects. Recruitment of potential subjects will be from the local San Antonio area. The subjects will be identified with code numbers (CP01 to CP15). The approval of the UTHSA IRB will be obtained. This study will be conducted in compliance with International Conference on Harmonization (ICH) Good Clinical Practice Guidelines. At the screening visit, each subject will complete a medical / dental history and read and sign an informed consent form. Following consent, a visual oral health exam will be performed by a licensed dentist. Subjects will be enrolled based on all the inclusion and exclusion criteria and other screening evaluations such as preliminary sialometry, and then randomly assigned to one of two treatment sequences.

Construction of the *in-situ* appliance

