The 3 blocks from each tooth will be used, as follows: two blocks with MIH lesions will be used for remineralization assessment and one healthy tooth block will serve as control for the MD of healthy enamel. The MIH-bearing blocks will be covered with polyester gauze (Bard Peripheral Vascular, Inc., USA), which will facilitate plaque retention on the surface of the tooth blocks on intra-oral exposure. Following recruitment, an impression of the subject's lower dentition will be taken using an alginate impression material. A dental technician will fabricate a lower removable intra-oral appliance. Each of the MIH-lesion-bearing blocks will be mounted on each side within the acrylic portion of the removable appliance, using Intermediate Restorative Material (IRM) cement (fluoride-free). All appliances are sterilized with ethylene oxide prior to delivery to the subject.

Test Product Description and Labeling

The toothpastes to be used for treatments are 10% HAP toothpaste, 1450 ppm NaF fluoride toothpaste, and non-fluoride toothpaste (washout). The 2 test products will be coded by the manufacturing/packaging company, who will retain the code until the completion of the study and data interpretation. The experiment will consist of two distinct treatment phases, Phase 1 and Phase 2, during which subjects will be exposed to one of the 2 products in a randomized crossover design, with each phase lasting for 2 weeks.

Study Procedure and Patient Instructions

Prior to each 2-week treatment phase, subjects will complete a 1-week washout period. This period allows for attenuation of any residual effect of the subject's previously used toothpaste. During this period, no appliance will be worn, and subjects will be using only the provided washout toothpaste and a soft-bristled toothbrush twice daily. Following the washout period, the intra-oral appliance will be fitted to each subject by a qualified dentist. Immediately after fitting of the first appliance (on day 1 of the first treatment phase), each subject will receive a soft bristled manual toothbrush for use throughout the duration of the study and a toothpaste according to the treatment phase. They will make the first use of the test product under the supervision of the study coordinator. For the remainder of the study, subjects will complete the procedure at home and as instructed.

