The subjects will be instructed to brush their teeth with the appliance in the mouth, two times daily, for 3 minutes on each brushing episode, in the morning after breakfast and last thing before bed, then rinsing with 10 ml of water. In dispensing the toothpaste onto the toothbrush, the subjects should fill the toothbrush surface from end to end but no more than one ribbon of toothpaste. The subjects will be advised not to brush directly on the blocks but rather to brush around the blocks to prevent disruption of the plaque. Subjects should neither eat nor take any drink for at least 30 minutes after brushing, they will be also instructed to remove the appliance while eating. A timer and measuring cup will be provided to each subject. To monitor product usage and compliance, a diary will be provided to each subject and checked at every visit, to record the number of tooth-brushings performed each day and the time it was done. Further, subjects will be instructed to return the remaining washout or test toothpaste after each treatment phase. The weight of toothpaste will be measured before and after each treatment phase. Over the study period, all subjects are to maintain their normal dietary habits.

On day 15, the subject, without using the product that morning, will arrive at the clinic, and the tooth block will be harvested and sent to the laboratory for μ CT analysis. Then the subject will be given washout toothpaste and a soft-bristle toothbrush to undergo another 7-day washout period without an appliance. After completion of the second washout period, subjects will return to the clinic, and the appliance, with another MIH-bearing tooth blocks mounted, will be fitted to the subject for the phase 2 treatment period. This procedure will then be repeated until the 2-week treatment phase is completed, and each subject has gone through the two arms of the study.

Upon completion of the treatment phases, the post-remineralization mineral density (MDt) of all the MIH-lesion-bearing blocks exposed intra-orally for remineralization will be assessed with μ CT. For the lesion-bearing blocks,

this process will yield the following information: the pre-test (MD_b) and post-test (MD_t) mineral density of the lesions and their associated images, while for the healthy tooth blocks, the MDs and the μ CT images.

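### The between-product paired t-test has no period term and no sequence balance is stated; a period-adjusted comparison is a cheap safeguard, though the planned test is not invalid

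*Combined protocol and SAP*

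**What the plan says.** Section D, Recruitment of Study Subjects, describes a crossover in which subjects are "randomly assigned to one of two treatment sequences". It gives no allocation ratio, block size or method of generating the list. Sample Size Calculation intends that "approximately 15 subjects complete all study treatments and be evaluable for the efficacy analysis", so no allowance is made for dropout.

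Statistical Analysis names one method for comparing MD, %ΔMD and %MDR: comparisons "between the two treatment groups as well as the intra-group comparisons will be performed using the paired Student's t-test". Data Handling adds that, for the product comparison, "percentage change in MD calculated relative to the control will be determined for each test product". No section mentions a period or sequence term.

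Study Procedure and Patient Instructions describes two 2-week phases, each after a 1-week washout. The washout is meant for "attenuation of any residual effect of the subject's previously used toothpaste". For phase 2 it says: "After completion of the second washout period, subjects will return to the clinic, and the appliance, with another MIH-bearing tooth blocks mounted".

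**The concern.** In a two-sequence crossover, any general difference between phase 2 and phase 1 enters the within-subject product difference with opposite signs in the two sequences. A paired t-test pools the sequences. It therefore treats the shift partly as a product effect, if the sequences are unequal in size, and partly as random error. With 15 subjects exact balance is impossible, and dropout could make the imbalance worse.

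The phases are not described as identical. Phase 1 follows the subject's own toothpaste and phase 2 follows a test product, each with one week between. The text on day 1 of the first phase says "They will make the first use of the test product under the supervision of the study coordinator", with home use afterwards. Phase 2 uses different blocks, and no rule assigns blocks to phases. At stake are power near an even split, and the accuracy of the estimate and p-value at an uneven one.

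**Working it through.** **Inputs.** From Sample Size Calculation: n = 15, product difference 8.1 points of %MDR, SD 12.6 (called within-subject), two-sided 5%, stated power 80%. From Recruitment of Study Subjects: two sequences, split not stated. The period effect p is not in the documents; 0, 4 and 8.1 points are assumptions.

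**1. The plan's own figure.** If 12.6 is the SD of the paired differences, SE = 12.6/√15 = 3.25 and the noncentrality is 8.1/3.25 = 2.49. With 14 df, power is 64%. If 12.6 is the SD per phase, the SD of differences is 12.6 × √2 = 17.8 and power is 37%. Neither gives 80%. That is a separate matter; here 64% and 37% are only the starting points.

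**2. What the paired t-test does with a period effect.** Write each subject's HAP-minus-fluoride difference as D = τ + p·s + e, with s = +1 for HAP in phase 2 (n1 subjects) and −1 for HAP in phase 1 (n2 subjects).

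- Mean of D = τ + p(n1−n2)/15. The share of p left in is 1/15 at 8:7, 3/15 at 9:6, 5/15 at 10:5 and 7/15 at 11:4. For p = 8.1 this is 0.54, 1.62, 2.70 and 3.78 points.
- Expected sample variance = σ² + p² × 4·n1·n2/(15 × 14). At 8:7 with p = 8.1 and σ = 12.6, this is 158.8 + 65.6 × 1.067 = 228.7, so the SD rises from 12.6 to 15.1.

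**3. What a period term does.** Regressing D on s gives an intercept equal to the average of the two sequence means, from which p cancels. Its SE is (σ/2)√(1/n1 + 1/n2) with 13 df. At 8:7 that is 6.3 × √(1/8 + 1/7) = 3.26, against 3.25 unadjusted.

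**4. Power at 8:7, effect 8.1** (simulated, 400,000 runs per case; the range covers both directions of p):

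| Assumed p | Paired t, SD 12.6 | Adjusted | Paired t, SD 17.8 | Adjusted |
|---|---|---|---|---|
| 0 | 64% | 63% | 37% | 37% |
| 4 | 57–63% | 63% | 34–38% | 37% |
| 8.1 | 42–54% | 63% | 27–34% | 37% |

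**5. Type I error of the paired t-test given the split, SD 12.6:**

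| Assumed p | 8:7 | 9:6 | 10:5 | 11:4 |
|---|---|---|---|---|
| 4 | 4.1% | 4.6% | 5.6% | 7.3% |
| 8.1 | 2.3% | 3.6% | 6.6% | 12.1% |

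The adjusted test gives about 5% in every cell. If allocation were simple randomisation (an assumption), 10:5 or worse would occur 30% of the time. Averaged over all splits, the paired t-test's type I error at p = 8.1 is 5.0%.

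**6. Price of the term.** With p = 0, effect 8.1 and SD 12.6 (exact noncentral t), power falls from 63.9% to 63.2% at 8:7, 61.7% at 9:6 and 58.4% at 10:5. These are losses of 0.7, 2.3 and 5.5 points (the last two from unrounded values). Averaged over simple randomisation, paired versus adjusted power is 64% v 60% at p = 0, 63% v 60% at 2, 62% v 60% at 3, 60% v 60% at 4 and 49% v 60% at 8.1. At SD 17.8 the two meet near p = 5 (both 35%).

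**The case against.** A paired t-test is an accepted analysis of a two-period crossover, and nothing in the documents shows that the phases differ. Each phase uses fresh blocks with their own measured baseline, and both phases follow a week on the same washout paste. Supervised first use is one brushing among about 28 (two a day for 14 days), and "This procedure will then be repeated until the 2-week treatment phase is completed" may mean that it recurs in phase 2. Haphazard assignment of blocks adds noise rather than a phase shift, and a period term would not remove it. Residue from a phase 1 product is carryover, which the term does not address either. The largest error rates need both a period effect as big as the target product difference and a badly uneven split.

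Most of this stands. A reader might infer that the planned test is invalid or inflates false positives. The documents do not support that, because the error rate averages 5% over randomisation and is below 5% near 8:7. A reader might also infer that a period term always recovers power. It does not: if allocation is unblocked and the period effect is small, it loses power on average.

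What the objection does not remove is that the trial is run once, at one split. At that split the unadjusted estimate carries whatever share of p the imbalance leaves in. The adjusted estimate does not, and near 8:7 the protection costs very little.

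**Conclusion.** The point holds as an inexpensive improvement, not as an error in the plan. The only between-product test omits period in a two-sequence design, and no balancing of the sequences is stated.

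The benefit depends entirely on a period effect that the documents do not give. At 8:7, with the effect at 8.1 and the SD of differences read as 12.6, the term gives up 0.7 points of power if the phases are alike. It avoids a loss of roughly 8 to 21 points (63% against 42–54%) if they differ by 8.1. At an assumed 4 points the difference is about 0 to 6 points (63% against 57–63%). If the phases barely differ, the gain is negligible.

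The two parts of the remedy belong together: the term protects the result at whatever split occurs, and balance keeps the term cheap.

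**What to change.** 1. Before unblinding, specify for %MDR and %ΔMD a regression of each subject's HAP-minus-fluoride difference on a sequence code (+1/−1). Report the intercept, which is the period-adjusted product difference, with a 95% CI on 13 df. This needs one value per subject and phase, as the paired t-test already does. Data Handling defines the quantities in %MDR as means without saying over what, so name that unit in the same sentence.
2. If randomisation has not begun, allocate sequences in blocks so that 15 subjects split 8:7. If it has begun, blocking can no longer be introduced by a statement in the plan; report the allocation method used and the split obtained.

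The cost is a few sentences of SAP wording, an ordinary regression in the software already named, one degree of freedom and, where still possible, a blocked list. No new data are needed. With no period effect the power cost is 0.7 points at 8:7, 2.3 at 9:6 and 5.5 at 10:5. If allocation was unblocked, the sponsor should accept that the term gains power on average only for period effects of about 4 points (SD 12.6) or 5 points (SD 17.8) or more. Its value below that is an unbiased estimate and a correct error rate at the split obtained.
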